6.5 Duration of Follow Up

Patients will continue to be followed for at least 30 days after the last dose of trial drug or until new anti-cancer treatment is initiated, whichever is earlier.

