Protocol Number/Title	CASE 6819 A Phase II Study of Intermittent Checkpoint Inhibitor Therapy In Patients With Advanced Urothelial Carcinoma
Study Phase	A Phase II study
Brief Background/Rationale	
Immunotherapy has revolutionized the treatment of patients with aUC. Five checkpoint inhibitors (CPI) (atezolizumab, pembrolizumab, avelumab, durvalumab, and nivolumab) are approved for relapsed/refractory aUC following platinum-based chemotherapy and 2 CPI (atezolizumab and pembrolizumab) are approved for cisplatin-ineligible patients. Duration of therapy required to sustain clinical benefit is unclear; patients are treated indefinitely until intolerable toxicity or disease progression.
 
Clinical trials investigating CPI in melanoma and kidney cancer have shown durable responses in patients who have discontinued therapy for reasons other than disease progression.^{1,2} Similarly, in the CheckMate275 trial of nivolumab in patients with aUC who progressed following platinum-based chemotherapy, 6 patients had sustained responses off therapy (4–12+ weeks).³ Likewise, in the phase 1/2 trial of durvalumab in aUC, a patient who discontinued treatment, unrelated to progression, maintained a response off therapy for >32 weeks.⁴
 
Although generally well tolerated, the indefinite continuation of CPI presents multiple challenges including cumulative toxicities and financial burdens. Novel dosing schedules, early discontinuation considerations, and biomarkers of response are needed to identify patients who can sustain disease regression while off of therapy.

Primary Objective	To assess the efficacy of intermittent CPI therapy, defined as the proportion of patients who remain off therapy for at least 36 weeks
Secondary Objective(s)	
 • To determine the clinical outcome (TFI, ORR, PFS, OS) in advanced urothelial carcinoma with intermittent CPI therapy, at 12 week intervals from when therapy is first held. • To assess response to re-initiation of CPI therapy.
Exploratory Objective(s)	n/a
Correlative Objective(s)	Tissue: Investigate the genomic and immunologic markers of response and resistance to therapy. [See Section 10.2]

	Blood: Investigate the immunomodulatory cell makeup [specifically, lymphocyte PD-1 occupancy, myeloid-derived suppressor cells (MDSC), regulatory T cells (Treg), CD4 and CD8 T Cells, TCR repertoire] at the start of treatment, during the intermittent phase and off treatment. [See Section 10.1]

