2.2 Secondary Objective(s)

[figure not shown]
- To determine the clinical outcome (TFI, ORR, PFS, OS) in advanced urothelial carcinoma with intermittent CPI therapy.
- To assess response to re-initiation of CPI therapy

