3.3 Expected Duration of Treatment and Subject Participation

Each study cycle consists of 14-28 days, depending on which CPI is chosen. CPI of choice will be administered on day 1.

All patients who do not meet criteria for the CPI intermittent phase of the study will be treated until unacceptable toxicity or RECIST-defined PD. Patients with RECIST-defined PD may continue CPI therapy at the discretion of the treating MD. These patients will continue with normal imaging every 12 weeks. In cases where a patient is continued on therapy after PD and develops subsequent PD ($\geq 20\%$ increase in sum of target lesions compared to the initial PD tumor measurements, the patient will come off study).

Patients who meet criteria for the intermittent phase (i.e., have $\geq 10\%$ tumor burden reduction) will not receive CPI therapy. Imaging will continue per protocol (every 12 weeks from the initial date they stopped CPI therapy). Patients who have RECIST defined PD on the intermittent phase should reinitiate CPI therapy. Patients who have a subsequent decrease in tumor burden $\geq 10\%$ can then restart CPI therapy as per protocol. (refer to schema in Section 3.1).

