6.4 Criteria for Removal from Study

Patients will be treated per protocol until:

1. RECIST-PD (treating MD may continue CPI). Study PI must be informed via email (or Site Communication Form") that subject is continuing based on clinical benefit. These patients will continue per normal imaging schedule (every 12 weeks).
2. Patients on CPI treatment who develop a RECIST-PD (PD1) can continue CPI treatment if there is clinical benefit. If on subsequent imaging they continue to have RECIST-PD (PD2), they will be removed from trial.
3. Unacceptable toxicity (see Section 7.3)
4. Withdrawal of consent
5. General or specific changes in the patients' condition that render the patient unacceptable for further treatment in the judgment of the investigator.
6. Any patient who on consecutive imaging (i.e., for 24 weeks) has SD while on therapy and does not achieve > 10% tumor burden reduction will be removed from the trial.

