8.2 Serious Adverse Events Definition

A Serious Adverse Event (SAE) is any untoward medical occurrence that at any dose:

- results in death
- is life-threatening (defined as an event in which the subject was at risk of death at the time of the event; it does not refer to an event which hypothetically might have caused death if it were more severe)
- requires inpatient hospitalization or causes prolongation of existing hospitalization (see NOTE below)
- results in persistent or significant disability/incapacity
- is a congenital anomaly/birth defect
- is an important medical event (defined as a medical event(s) that may not be immediately life-threatening or result in death or hospitalization but, based upon appropriate medical and scientific judgment, may jeopardize the subject or may require intervention [eg, medical, surgical] to prevent one of the other serious outcomes listed in the definition above.) Examples of such events include, but are not limited to, intensive treatment in an emergency room or at home for allergic bronchospasm; blood dyscrasias or convulsions that do not result in hospitalization.)
- Potential drug induced liver injury (DILI) is also considered an important medical event.
- Suspected transmission of an infectious agent (eg, pathogenic or nonpathogenic) via the study drug is an SAE.
- Although pregnancy, overdose, and cancer are not always serious by regulatory definition, these events must be handled as SAEs.

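### OS is a secondary endpoint, but required contact after removal ends within 30 days of the last CPI dose or at new therapy, so later OS may be overestimated if patients are censored there

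*Combined protocol and SAP*

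**What the plan says.** Section 2.2 sets a secondary objective: "To determine the clinical outcome (TFI, ORR, PFS, OS) in advanced urothelial carcinoma with intermittent CPI therapy". The synopsis adds a reporting schedule, "with intermittent CPI therapy, at 12 week intervals from when therapy is first held", with no end date. Section 14.4 plans Kaplan-Meier estimates for survival endpoints and Cox models relating them to clinical factors and biomarkers. It gives neither a time origin nor a censoring rule for OS.

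While on study, patients are seen at each treatment cycle or, off therapy, every 12 weeks (section 11.0, footnote 13). Progression on the break does not end participation: "Patients who have RECIST defined PD on the intermittent phase should reinitiate CPI therapy" (section 3.3).

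After removal, section 6.5 requires that patients be "followed for at least 30 days after the last dose of trial drug or until new anti-cancer treatment is initiated, whichever is earlier". Footnote 15 of the calendar repeats this limit and accepts contact by phone. The post-study column lists adverse events and clinically indicated imaging only.

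Reasons for removal in section 6.4 include unacceptable toxicity, changes that "render the patient unacceptable for further treatment in the judgment of the investigator", and repeated progression on CPI: "If on subsequent imaging they continue to have RECIST-PD (PD2), they will be removed from trial". Footnote 14 allows the removal visit to be one at which no drug is given.

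An SAE includes an event that "results in death" (section 8.2). Section 8.5 collects SAEs for 30 days after dosing stops or until the next treatment. After that it asks only for those believed related to study drug or a protocol procedure.

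**The concern.** The follow-up clock suits a trial of continuous dosing. Here the intervention is withholding CPI, and the clock runs from the last dose. A patient removed during the break may therefore have no required contact after removal. A later cancer death not thought related to treatment is not picked up by SAE reporting either.

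Kaplan-Meier and Cox both assume that patients censored at a given time have the same outlook as those still followed. Patients who leave for a second progression, toxicity or worsening condition probably do not. If they are censored on leaving, their later deaths drop out and the curve is held up by those doing well. At stake are the later part of the OS curve and the biomarker models, which would have few deaths even with complete follow-up.

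**Working it through.** The plan states no OS figure, so there is nothing of its own to reproduce. The check has three parts.

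**1. The clock.** The first scheduled off-therapy visit is 12 × 7 = 84 days after the hold, and the optional interim visit is at 6 × 7 = 42 days. Both fall beyond 30 days from the last dose.

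**2. True OS in an illustrative model.** Inputs from the documents:
- 40% progression within one year (section 14.2);
- 6.8-month median survival after progression (section 1.2.2, post-platinum atezolizumab patients moved to other treatment, so not this population).

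Assumed: exponential times, no death before progression, and a 24-month horizon, which is not the protocol's.
- Progression rate a = −ln(0.6)/12 = 0.0426 per month.
- Death rate after progression b = ln(2)/6.8 = 0.1019 per month.
- S(t) = [b·exp(−at) − a·exp(−bt)]/(b − a).
- S(24) = (0.10193 × 0.360 − 0.04257 × 0.0866)/0.05936 = 0.556.
- Expected deaths in 20 patients: 20 × (1 − 0.556) = 8.9.
- 95% half-width with complete follow-up: 1.96 × √(0.556 × 0.444/20) = 0.22.

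**3. Kaplan-Meier if patients are censored at last required contact.** By simulation: progression on the break is found at the next 12-weekly scan, CPI is restarted, and the patient leaves at the second progression (PD2). Contact ends that day if new therapy starts, or 30 days later.

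| Exit pattern | 24-month estimate | Bias | Deaths seen of 8.9 |
|---|---|---|---|
| All leave at PD2, 12 weeks on, new therapy that day | 0.74 | 0.18 | 4.2 |
| Same, 30 more days | 0.71 | 0.15 | 4.9 |
| All leave at PD2, 24 weeks on, new therapy that day | 0.66 | 0.10 | 5.9 |
| Same, 30 more days | 0.64 | 0.08 | 6.4 |
| All leave at PD2, 36 weeks on | – | 0.05 to 0.06 | – |
| Half of progressors stay on study after restart (assumed) | – | 0.04 to 0.08 | – |
| Half of patients may also leave at a random time between progression and death, with no later contact (assumed) | – | 0.25 to 0.30 | – |

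Earlier landmarks, first four rows: 0.00 at 12 and 24 weeks, 0.00 to 0.02 at 36, 0.01 to 0.04 at 48, and 0.04 to 0.10 at 72. In the last row the bias is already about 0.025 at 24 weeks and 0.05 at 36.

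Sensitivity of the first four rows at 24 months:
- One-year progression of 30% to 60% with medians of 6.8 to 8.6 months: 0.07 to 0.22.
- A 1.2-month median: 0.04 or less.
- Half of post-exit deaths learned anyway: 0.03 to 0.06.
- All such deaths learned, but survivors still censored at last contact: −0.02 to −0.04.

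As a control, a run with removal unrelated to prognosis gave 24-month OS of 0.486 with full follow-up and 0.487 with censoring. The bias therefore comes from the link between removal and prognosis.

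**The case against.** The strongest reply is that the bias is conditional. Thirty days is a floor, section 14.4 tells no one to censor at last required contact, and a sponsor that lists OS as an objective may well collect death dates. That stands. A reader might infer that the plan prescribes a biased OS analysis, but the documents do not say so. What they do is require nothing more, which leaves OS dependent on what sites happen to learn. Uneven knowledge is not neutral either: learning every death while censoring survivors early biases OS slightly downward.

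A second reply is that 0.08 to 0.18 assumes every patient who progresses on the break fails the restart. This also stands. Section 3.3 provides for a further reduction in tumour burden after restart, and response to re-initiation is itself an objective, so the lower figures are plausible.

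A reader might equally infer that OS up to 24 weeks is safe. That holds only if PD2 is in practice the sole exit. Section 6.4 also removes patients for toxicity or worsening condition, and either can happen early.

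Finally, OS is descriptive in 20 patients, and its half-width of 0.22 exceeds most of these biases. True, but the confidence interval shows the imprecision and does not show the bias.

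**Conclusion.** The gap holds on the text: OS is an endpoint, and the plan requires no survival contact after removal beyond the earlier of 30 days from the last CPI dose or new therapy. Upward bias follows if sites stop at that minimum, censor there and do not learn of later deaths.

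Its size cannot be derived from the documents. Across the illustrated exit patterns, the 24-month overestimate runs from about 0.04 to 0.30 with no passive learning of deaths and a 6.8-month post-progression median. A differently built model, with other assumptions about removal and a 36-month cut-off, gave 0.10 to 0.53. No single figure should be read as a prediction. Early landmarks are little affected if PD2 is the main exit, but they are not guaranteed unbiased.

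A reader might carry this over to the main result. That is not supported: the 36-week primary endpoint and the 24-week safety rule rest on on-study assessments. The point is worth fixing because the remedy is cheap and death dates not recorded at the time may be hard to recover.

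**What to change.** In section 6.5, footnote 15 and the post-study calendar column, require vital status by phone or chart about every 12 weeks for every patient who entered the intermittent phase. Continue regardless of removal or new therapy until death, withdrawal of consent or study close. Record the start date of any new anti-cancer therapy.

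In section 14.4, define OS from the date CPI is first held. This fits the synopsis reporting schedule, which does not itself state an OS origin. State that OS is not censored at removal or at new therapy, and that survivors are censored at the last date known alive from the scheduled checks.

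The cost is one amendment and modest coordinator time for about 20 patients. OS will then include the effect of later therapies, which should be said when it is reported. The change makes OS descriptively valid. In a single arm it still cannot show whether stopping CPI affects survival.

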8.4 Adverse Event Evaluation

The collection of Grade ≥ 2 AE and SAE information should begin at initiation of study drug. All non-serious adverse events (not only those deemed to be treatment-related) should be collected continuously during the treatment period and for a minimum of 30 days following the last dose of study treatment or until next treatment is initiated, whichever comes first.

Baseline physical and laboratory Grade ≥ 2 AEs should be followed to resolution or stabilization or reported as SAEs if they become serious. Follow-up is also required for non-serious AEs that cause interruption or discontinuation of study drug and for those present at the end of study treatment as appropriate.

A laboratory test abnormality considered clinically relevant (e.g., causing the subject to withdraw from the study, requiring treatment or causing apparent clinical manifestations, result in a delay or dose modification of study treatment, or judged relevant by the investigator), should be reported as an adverse event.

The investigator or sub-investigator (treating physician if applicable) will provide the following for all adverse events (both serious and non-serious):

- Event term (as per CTCAE)
- Description of the event
- Date of onset and resolution
- Expectedness of the toxicity
- Grade of toxicity
- Attribution of relatedness to the investigational agent- (this must be assigned by an investigator, sub-investigator, or treating physician)
- Action taken as a result of the event, including but not limited to; no changes, dose interrupted, reduced, discontinued, etc. or action taken with regard to the event, i.e. no action, received conmed or other intervention, etc.
- Outcome of event

Descriptions and **grading scales** found in the NCI Common Terminology Criteria for Adverse Events (CTCAE) version 5.0 will be utilized for AE reporting. (for more information, please see

https://ctep.cancer.gov/protocolDevelopment/electronic_applications/ctc.htm#ctc_50)

An **expected adverse event** is an event previously known or anticipated to result from participation in the research study or any underlying disease, disorder, or condition of the subject. The event is usually listed in the Investigator Brochure, consent form or research protocol.

An **unexpected adverse event** is an adverse event not previously known or anticipated to result from the research study or any underlying disease, disorder, or condition of the subject.

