11.0 STUDY PARAMETERS AND CALENDAR

	Screening (≤ 4 weeks prior to dosing)	Cycle 1 Day1 (+/- 3 days) ¹ *	Cycle 2+ D1 (+/- 2 or 3 days) for patients on therapy and for patients re- starting therapy ^{2*}	Patients OFF therapy: every 6 weeks (+/- 3 days) ¹³	Patients OFF therapy: Every 12 weeks (+/- 3 days) ¹³	End of Treatment (+/- 3 days) ¹⁴	Post Study follow up(+/- 3 days) ¹⁵
Informed Consent	X						
ECOG PS, Weight (screening only), Vital Signs	X	X	X	X	X	X	
History/Physic al ³	X	X	X	X	X	X	
Adverse Events		X	X	X	X	X	X
Hematology ⁴	X	X	X	X	X	X	
Chemistry ⁵	X	X	X	X	X	X	
TSH, T4, T3 ⁶	X		X		X		
Autoimmune labs ⁷	X						
Correlative Studies ⁸	X		X		X		
CPI		X	X				
Tumor Imaging ⁹	X		X		X	As clinically indicated	As clinically indicated
Brain CT or MRI ¹⁰	As clinically indicated		As clinically indicated		X	As clinically indicated	As clinically indicated
Bone Scan ¹¹	As clinically indicated		As clinically indicated		X	As clinically indicated	As clinically indicated
Biopsy ¹²				X			

*One Cycle is 14-28 days. Visit window +/- 3 days for Atezolizumab, Nivolumab, and Pembrolizumab. Visit window is +/- 2 days for Avelumab and Durvalumab.

1. Cycle 1 Day 1 Hematology, chemistry, autoimmune labs, and physical exam need not be repeated if done within 14 days

2. History, physical, AEs, Hematology, Chemistry to be done D1 (+/- 3 days) of every cycle

3. Baseline exam should be comprehensive. Subsequent physical exams can be targeted exams.

4. Hematology: CBC with differential, hemoglobin, hematocrit, platelets
5. Blood chemistry: sodium, potassium, chloride, bicarbonate, BUN, creatinine, albumin, total albumin, bicarbonate, AST, ALT, glucose, LDH (baseline only)
6. TSH, T4, T3: Screening, and on all imaging days, then as clinically indicated.
7. Autoimmune labs ANA by IFA screen, Anti-ENA, Anti-DNA DS, Rheumatoid factor, CCP antibody, ESR, CRP. These only need to be drawn if not drawn prior to initial treatment with CPI therapy.
8. Correlative studies: Correlative studies will be drawn with blood draws at biopsy, screening and prior to each imaging.
9. Tumor imaging: CT of the chest, abdomen, and pelvis (with contrast, if possible) to be performed to assess disease status at screening, and every 12 weeks from Cycle 1 Day 1. Tumor imaging should also be done whenever disease progression is suspected and as clinically indicated.
10. Brain imaging Brain CT or MRI scan to be performed as clinically indicated.

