11. Bone imaging: Bone scan to be performed if clinically indicated.
12. Biopsy is recommended at any time during cycle 1 (for PR and SD patients) and within 3 weeks of any other time period at which a PD or PR is achieved in any patient (unless not feasible or unsafe per investigator discretion. Archival tissue up to 6 months prior to enrollment is acceptable in lieu of a cycle 1 biopsy
13. OFF treatment Patients will be seen every 12 weeks. The 6-week interim visit between scans will be done if clinically indicated. Labs during the 6-week interim visit should be as clinically indicated.
14. End of treatment: End of treatment visit is defined as the visit during which the patient will be removed from the study (even if not receiving drug at that visit).
15. Post- study follow up Patients will continue to be followed for at least 30 days after the last dose of CPI therapy or until new anti-cancer treatment is initiated, whichever comes first. Phone follow-up is sufficient.

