14.4 Analysis Plan

Summary statistics of toxicity and success status will be provided in frequencies and percentages. Toxicity and success rates will be estimated along with 95% CIs. Logistic regression model will be used to explore effects of patient and tumor characteristics on toxicity or success status. Survival endpoints will be estimated by Kaplan-Meier method and compared by log rank test. Cox proportional hazard model will be used to associate clinical factors and biomarkers with survival endpoints. Other statistical analyses will be carried out as appropriate.

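### Overall survival is a secondary outcome, but required follow-up after a patient leaves the trial ends 30 days after the last CPI dose, or at new therapy if earlier

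*Combined protocol and SAP*

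**What the plan says.** The synopsis lists TFI, ORR, PFS and OS as secondary outcomes "with intermittent CPI therapy, at 12 week intervals from when therapy is first held". Section 2.2 repeats the four outcomes without a time origin. Section 14.4 says "Survival endpoints will be estimated by Kaplan-Meier method" and gives no censoring rule for OS.

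On follow-up, 6.5 says patients are "followed for at least 30 days after the last dose of trial drug or until new anti-cancer treatment is initiated, whichever is earlier". Note 15 to the calendar in 11.0 repeats the limit, as "followed for at least 30 days after the last dose of CPI therapy or until new anti-cancer treatment is initiated, whichever comes first", and adds that a phone call is enough. The calendar's column headed "Post Study follow up" contains adverse events, plus tumor, brain and bone imaging as clinically indicated. It has no row for survival status.

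Patients who are off CPI but still on study are seen every 12 weeks (note 13). Section 6.4 lists the ways out of the trial: second progression on CPI ("If on subsequent imaging they continue to have RECIST-PD (PD2), they will be removed from trial"), toxicity, withdrawal of consent, the investigator's judgement of the patient's condition, and prolonged stable disease without more than 10% shrinkage. Note 14 allows for the removal visit to take place while the patient is not receiving drug.

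**The concern.** The window in 6.5 closely matches the adverse-event window in 8.4 ("for a minimum of 30 days following the last dose of study treatment or until next treatment is initiated, whichever comes first"). That suits safety reporting but not OS, for two reasons. The clock starts at the last dose, although the strategy under test is to withhold doses. It also stops at new anti-cancer treatment, although survival continues to matter after a switch.

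Several exits are tied to prognosis: second progression, clinical decline, and stable disease without the required shrinkage. Other antineoplastic therapy is prohibited on study (6.3), so a change of treatment in practice ends participation too. If OS is censored at these points, patients who leave are treated as having the same future survival as those who stay. Kaplan-Meier depends on that assumption, and it is unlikely to hold here. If most exits were disease-driven, the curve would tend to read too high.

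**Working it through.** The plan gives no event count, precision or follow-up time for OS, so there is no OS figure to reproduce. The nearest design figure is the half-width in 14.3. With n = 20 the exact (Clopper-Pearson) 95% interval is widest at 10/20, with half-width 0.228. This agrees with the stated limit of 0.23 and does not depend on follow-up after exit.

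**Inputs**

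- Required follow-up: 30 days from last dose (6.5, note 15), which is 30/7 = 4.3 weeks, cut short by new anti-cancer treatment.
- Time zero for OS: the date CPI is first held (synopsis).
- Off-therapy scans: every 12 weeks from that date (3.3).
- Spacing of OS time points: 12 weeks (synopsis).
- Patients in the intermittent arm: 20 (3.2).

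**Formula.** Required follow-up after exit = max(0, week of last dose + 4.3 − week of exit), or less if new therapy starts first.

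**1. Patient leaves off therapy without re-starting CPI.** The last dose is at or before week 0, so the window closes by week 4.3. The first off-therapy scan is at week 12, which is 12 − 4.3 = 7.7 weeks later. For an exit at week t ≥ 12, max(0, 4.3 − t) = 0.

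**2. Patient removed at second progression after re-starting, or permanently discontinued for toxicity.** CPI stops (3.1 footnote 2; 7.3), so the last dose is at or before removal. Required follow-up is at most 4.3 weeks. That is 4.3/12 = 36% of one OS interval, and 7.7 weeks short of a full one. At most one further 12-weekly OS time point can fall inside it.

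**3. Patient removed for stable disease (6.4, item 6).** As worded, this item also reaches patients who re-started CPI. CPI may continue as standard of care outside the trial, so the date of the last dose is unknown and no end date can be given.

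**Scale of the effect on an OS proportion.** If k of 20 patients have unknown status at a time point, the estimate with all k alive and the estimate with all k dead differ by k/20:

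| k | Best-to-worst range |
|---|---|
| 1 | 5 points |
| 2 | 10 points |
| 4 | 20 points |

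The Kaplan-Meier estimate lies inside this range. The range is therefore a bound, not an estimate of bias.

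**What cannot be computed.** The documents give no rate of leaving the trial. The 40% expected to progress within one year (14.2) cannot stand in for it, because progression off therapy leads to re-starting CPI on study (3.3), not to removal.

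**The case against.** The strongest reply is that the plan is silent on OS after exit and does not prescribe censoring. The words in 6.5 set a minimum, nothing forbids later ascertainment, and 13.2.2 already has patients authorise access to relevant hospital records. On-study follow-up is also long. Off-therapy patients are seen every 12 weeks with no stated end, progression off therapy leads to re-treatment, and progression on CPI may be treated through. Deaths during all of this would be recorded. All of that stands, and it limits the problem to the time after exit.

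Three narrower points also have weight. Section 6.4 mixes stopping treatment with leaving the trial, and a switch of therapy is not itself listed there as a removal criterion. The 12-weekly OS schedule from first hold appears only in the synopsis. The calendar places post-study follow-up after the removal visit, so a contact counted from removal may have been intended for patients already off drug. Even on that reading, the required time is 30 days, or 4.3 weeks, as in case 2.

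None of this supplies a survival contact. Permission to follow longer is not a requirement, and practice may then differ between patients and sites. If 6.5 was meant for safety alone, OS has no collection rule after exit at all.

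**Conclusion.** The concern holds. As written, required follow-up after exit is zero for a patient who leaves off therapy at week 12 or later without re-starting. It is at most 4.3 weeks after second progression on CPI or permanent discontinuation for toxicity, and less if new therapy starts. Each patient of unknown status adds 5 points to the range of possible OS proportions at N=20. The number of such patients and the direction of bias cannot be derived from the documents.

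The effect is confined to secondary outcomes. The primary endpoint, sample size, interval half-width and stopping rules do not change. The conclusion takes 6.5 and note 15 literally and assumes that no survival contact is set out in the parts not available for this check: the schema drawing in 3.1, Registration (5.0, going by the contents list) and the specimen address (10.3). A survival rule in any of these is unlikely.

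**What to change.** In 6.5 and calendar note 15, state that for every patient who entered the intermittent arm, neither removal from the trial nor the start of new therapy ends collection of survival status. Progression status should also continue to be collected for patients who have not yet progressed, since PFS is listed in the same objective. Collect both by phone or chart every 12 weeks until death, withdrawal of consent or study close, and define study close. Add a survival-status row to the calendar's post-study column. Keep the 30-day window for adverse events.

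The cost is a wording change plus one brief contact or chart check every 12 weeks for about 20 patients. Note 15 already accepts phone follow-up. Survival status that is not collected during the trial may be hard to recover later.
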